9.4. Randomization and Blinding

This study will be conducted in a double-blind, placebo-controlled manner. Allocation to one of two treatment groups (OCA or placebo) will occur on a 1:1 ratio across sites and will be stratified by UDCA treatment (yes/no) and mean baseline bilirubin categories ($>ULN/\leq ULN$), as specified by the central laboratory. The randomization will be based on a predefined randomization code (generated by the Sponsor or designee) using an interactive web response system (IWRS), which the Sponsor intends will serve as a computer-based subject registration system at Screening and Day 0. The IWRS will serve as an investigational product inventory and management system and may be integrated with the study database.

The Investigator or designee will be required to register the subject in the IWRS and may be prompted to provide subject data necessary to properly randomize and allocate the subject to treatment. A randomization number will be assigned (refer to [Section 9.5.2](#) below) and investigational product dispensing information (ie, bottle number[s]) will be provided.

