13.1.3. Primary Efficacy Analysis

The primary efficacy endpoint will be the time to first occurrence of one of the following post-randomization:

- Death (all-cause)
- Liver transplant

- MELD score ≥ 15
- Hospitalization (as defined by a stay of 24 hours or greater) for new onset or recurrence of:
 - Variceal bleed
 - Hepatic encephalopathy (as defined by a West Haven score of ≥ 2)
 - Spontaneous bacterial peritonitis (confirmed by diagnostic paracentesis)
- Uncontrolled ascites (diuretic resistant ascites requiring therapeutic paracentesis at a frequency of at least twice in a month).
- Hepatocellular carcinoma confirmed by 2 complimentary imaging modalities unless confirmed by biopsy

The primary efficacy analysis will compare randomized OCA to randomized placebo with respect to the primary efficacy endpoint using the ITT population. Only adjudicated events will be included in analyses. The 2 treatment groups will be compared using the log rank test stratified by the randomization stratification factor. Kaplan-Meier (KM) estimates of the distribution of the time-to-event will be tabulated and graphed by treatment group. The tabulation will include the KM estimate of the medians and corresponding 95% confidence intervals (CIs), if the medians can be estimated. The number and percent of subjects censored and with events will be presented. The hazard ratio and 95% CI will be determined based on a Cox regression model stratified by randomization strata to estimate the magnitude of the effect.

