13.1.4. Key Secondary Efficacy Analyses

The key secondary efficacy endpoints will compare OCA to placebo on the following:

- Time to first occurrence of MELD score ≥ 15
- Time to liver transplant or death (all-cause)
- Change from Baseline in total bilirubin at end of study
- Change from Baseline in ALP at end of study

The key secondary efficacy analyses will compare randomized OCA to randomized placebo in ITT population with respect to the key secondary efficacy endpoints. Only adjudicated events will be included in time-to-event analyses. The comparison (hypothesis testing) will be conducted as specified in [Section 13.1.10](#) in a sequential closed testing gate-keeping procedure, provided that the primary efficacy endpoint comparison is statistically significant in favor of the OCA treatment group. If the primary comparison is not statistically significant then comparison of the secondary endpoints will be considered as descriptive and exploratory. This procedure controls the study-wise type I error.

The 2 treatment groups will be compared using the same methodology as specified for the primary efficacy analysis ([Section 13.1.3](#)).

Analyses of change from Baseline to end of study in ALP and total bilirubin will be compared between treatment groups using analysis of covariance (ANCOVA) with change from Baseline as the dependent variable including treatment group and randomization stratification factor as

fixed effects and the Baseline values as a covariate. The same analysis will be carried out using percentage change from Baseline as the dependent variable.

Descriptive statistics of the laboratory values will be summarized by treatment group. The results, change from Baseline, and percentage change from Baseline values as well as estimates of least-square means, standard errors, and 95% CIs will be presented by treatment group. Estimates of the mean difference between treatment groups, the standard error of the difference, and 95% CI of the difference will be presented.

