13.1.5. Additional Secondary Efficacy Analyses

The following time to event secondary efficacy analyses will compare randomized OCA versus randomized placebo using the ITT population:

- Time to each component of the primary efficacy endpoint (except MELD score ≥ 15 which is captured above)
- Time to development of varix/varices
- Time to liver-related death
- Time to liver-related death or liver transplant
- Time to liver-related death, liver transplant, or MELD score ≥ 15

The same analysis methodology as used for the primary efficacy analysis will be used for these secondary efficacy analyses. Similar endpoints, where available, will be analyzed to compare OCA to historical controls as described below in [Section 13.1.8](#).

Analyses of changes in liver biochemistry (GGT, ALT, AST, conjugated bilirubin, albumin, and INR) will be summarized and analyzed using the same methodology as specified in [Section 13.1.4](#) for the key secondary analyses of change in ALP and total bilirubin.

Progression to cirrhosis will be assessed in the subset of subjects considered non-cirrhotic at baseline using available medical history, clinical, and laboratory assessments as well as baseline TE, where available. Specifically, subjects with no clinical, laboratory, or radiological evidence of cirrhosis at baseline and/or a TE liver stiffness of < 16.9 kPa ([Corpechot 2012](#)) will be considered non-cirrhotic (See [Section 9.7.3.1](#)). Progression to cirrhosis will be assessed by the development of clinical, laboratory, or radiological evidence of cirrhosis and/or when liver stiffness increases to ≥ 16.9 kPa during the trial in which case histological progression to cirrhosis should be confirmed by biopsy unless not medically indicated. Using this definition for progression to cirrhosis, the percentage of non-cirrhotic subjects progressing to cirrhosis during the treatment period will be summarized by treatment group and compared using a Cochran–Mantel–Haenszel test stratified by the randomization stratification factor.

Analyses for the histological assessment conducted as part of the biopsy sub-study are defined in [Appendix C](#)).

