Analyses of changes in MELD score, Child-Pugh score, Mayo Risk Score (MRS), IgM, CRP, TNF- α , FGF-19, CK-18, C4, and ELF score will be summarized and analyzed using the Wilcoxon Rank Sum Test to compare treatment groups. The median differences and 95% CI of the median differences between treatment groups will be constructed using Hodges-Lehmann

estimate. If the median differences between treatments are not symmetrical around the median, the Sign Test may be used.

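### Changes in MELD, Child-Pugh, Mayo Risk Score and the biomarkers are compared by an unstratified rank-sum test after stratified randomization, which costs precision wherever the strata predict the change

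*Protocol*

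**What the plan says.** Section 9.4 sets up 1:1 allocation "stratified by UDCA treatment (yes/no) and mean baseline bilirubin categories", split at the upper limit of normal (ULN). That gives four strata.

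Most analyses of the randomized arms then use the strata:
- Primary endpoint (Section 13.1.3): "The 2 treatment groups will be compared using the log rank test stratified by the randomization stratification factor", with a Cox model on the same strata. The key and additional time-to-event endpoints follow this method.
- ALP and total bilirubin (Section 13.1.4): ANCOVA "including treatment group and randomization stratification factor", plus the baseline value. Section 13.1.5 extends this to GGT, ALT, AST, conjugated bilirubin, albumin and INR.
- Progression to cirrhosis (Section 13.1.5): a Cochran-Mantel-Haenszel "test stratified by the randomization stratification factor". The responder analyses in Section 13.1.6.1 use the same test.

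The last paragraph of Section 13.1.5 departs from this. Changes in MELD, Child-Pugh, Mayo Risk Score, IgM, CRP, TNF-α, FGF-19, CK-18, C4 and ELF are "analyzed using the Wilcoxon Rank Sum Test to compare treatment groups", and the "95% CI of the median differences between treatment groups will be constructed using Hodges-Lehmann" method. Neither sentence mentions strata, and baseline enters only through the subtraction that forms the change.

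Section 13.1.10 places these endpoints outside the gatekeeping hierarchy and makes their tests descriptive and exploratory.

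**The concern.** Stratified randomization balances the arms on UDCA use and bilirubin, which removes some of the chance variation in the treatment comparison. An unstratified rank-sum test computes its null variance as if that variation were still present. If the strata predict the outcome, the variance is overstated, the true error rate falls below the nominal level, and the Hodges-Lehmann interval is wider than the data require.

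For the scores there is reason to expect some prediction. Bilirubin is a scored item of Child-Pugh (Section 9.7.4, Table 6) and an input to the Mayo Risk Score (Section 9.7.5). MELD is computed from serum chemistry and coagulation (Section 12.2.7). Child-Pugh has a floor of 5, so the room to improve depends on the starting value. For the seven biomarkers the document gives no basis for a view either way.

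At stake is the precision of comparisons that serve the secondary objective on disease progression (Section 6.2).

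**Working it through.** **The plan's own figure.** The main-trial power statement concerns the primary endpoint only; no power or precision is given for the rank-tested endpoints. Inputs from Section 13.1.2: hazard ratio 0.60, two-sided 5%, 1:1, placebo survival 0.6 at 8 years, 4 years of accrual plus 6 of follow-up.
- Fixed-design events (Schoenfeld): 4(1.960 + 0.842)² / (ln 0.60)² = 4 × 7.85 / 0.261 ≈ 120.3, so 121.
- Power with 127 events: 82.1% fixed, and 81.3% with Lan-DeMets O'Brien-Fleming looks at 50% and 75%.
- Subjects: mean event probability (0.398 + 0.263)/2 = 0.331; 127/0.331 ≈ 384; 384/0.90 ≈ 427 with the 10% dropout in the Version 4 synopsis, against 428 stated.

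The figure reproduces and does not depend on the point at issue.

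**The rank-sum comparison.** From the document: 428 subjects, 1:1, four strata. Assumed, because the document does not give them: R², the share of outcome variance explained by the strata; 90% on UDCA; 50% or 30% with bilirubin above ULN; a treatment shift of 0.27 SD. The 30% equals the minimum set in the Version 4 synopsis.

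For a rough analytic check, true type I error is about 2[1 − Φ(1.96/√(1 − R²))] and the interval-width ratio is about 1/√(1 − R²):
- R² = 0.05: 1.96/√0.95 = 2.011, so 4.4%; width ratio 1.03.
- R² = 0.10: 1.96/√0.90 = 2.066, so 3.9%; 1.05.
- R² = 0.20: 1.96/√0.80 = 2.191, so 2.8%; 1.12.
- R² = 0.30: 1.96/√0.70 = 2.343, so 1.9%; 1.20.

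Simulation compared the unstratified rank-sum test with the van Elteren test (8,000 null and 4,000 alternative trials per setting), and the pooled with the stratum-aligned Hodges-Lehmann interval (300 trials). Error and power are averaged over the two bilirubin splits:

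| R² | Type I error, unstratified / stratified | Power, unstratified / stratified | Unstratified interval wider by |
|---|---|---|---|
| 0 | 4.8% / 4.8% | 77% / 77% | 0% |
| 0.02 | 5.0% / 5.1% | 79% / 79% | 1-2% |
| 0.05 | 4.3% / 5.0% | 79% / 80% | 3% |
| 0.10 | 3.8% / 5.0% | 79% / 81% | 6% |
| 0.20 | 2.9% / 5.1% | 80% / 86% | 13% |
| 0.30 | 1.9% / 4.9% | 81% / 90% | 21-22% |

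Simulated and analytic values agree closely.

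**On a more familiar scale.** With a fraction p above ULN and a between-stratum difference of d within-stratum SDs, R² = p(1 − p)d² / [1 + p(1 − p)d²]. With p = 0.40 (assumed), p(1 − p) = 0.24, so:
- d = 0.5: R² = 0.06/1.06 = 0.057.
- d = 0.75: R² = 0.135/1.135 = 0.119.
- d = 1.0: R² = 0.24/1.24 = 0.194.

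The formula above then gives type I errors of about 4.4%, 3.7% and 2.9%.

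**The case against.** The case for leaving the text alone has five parts.
- **Exploratory status.** The endpoints carry no stated power and sit outside the hierarchy. This stands and limits the priority. It does not explain the departure: the responder analyses are exploratory too and are stratified, and the additional liver biochemistry is outside the hierarchy yet adjusted for strata and baseline.
- **Validity.** A conservative test is still valid, so this is a matter of efficiency. This stands.
- **Level versus change.** Bilirubin entering a score shows that strata differ in its level, not in its change. This stands as a caution, and is why the loss can only be stated conditionally.
- **A matter for the SAP.** Section 13 leaves detail to the SAP, which is not shown. This carries less weight, because the protocol itself names the test and the estimator.
- **Version.** The text is Version 3.1. Version 4 follows in the file, but its Section 13 is not shown, so whether the wording persists cannot be checked. This stands.

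A reader might infer more than the document supports. One inference is that power is certainly lost and real effects will be missed. The document gives no R² for any of these endpoints, and at R² = 0 there is no loss. Another is that this is the only analysis without the strata. The Cox models for the proportion of treatment effect explained (Section 13.1.5.1) and the mixed-model sensitivity analysis (Section 13.1.9.2) name none either.

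**Conclusion.** The point holds as a minor matter of efficiency and consistency. The named test ignores strata that the design imposes and that nearly all other comparisons of the randomized arms use. The direction is certain only where the strata predict the change, and there the error is on the conservative side.

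If the strata explain 5% of the variance or less, the loss is negligible. At 10% it is noticeable but small, and only at 20-30% does it become material. These sizes rest on the assumed R², UDCA and bilirubin splits and treatment shift. They say nothing about whether a given marker is in the low or the high range.

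Nothing here touches the primary analysis, the gatekeeping, the 127 events or the 428 subjects.

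**What to change.** Replace the rank-sum test with a van Elteren test stratified by the randomization factors (UDCA use by bilirubin category), and report a stratum-aligned Hodges-Lehmann estimate with its 95% interval. A rank ANCOVA with strata and baseline as covariates is an equally good choice and would also bring these endpoints into line with the ANCOVAs in Section 13.1.4.

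The cost is a change of wording. The stratum variables are already recorded and standard software suffices. The simulation shows practically nothing given up when the strata are uninformative (77% power either way at R² = 0), even with only about 43 subjects off UDCA (10% of 428, as assumed). If Version 4 or the SAP already specifies a stratified form, no action is needed beyond confirming it.

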9. TREATMENT OF SUBJECTS

9.1. Investigational Product Treatment Regimen

The term investigational product refers to either OCA (provided as part of this clinical study) or matching placebo.

Two treatment groups will be evaluated: OCA and placebo. Investigational product will be administered orally. Each dose will be made up of 1 tablet (ie, one 5 mg OCA tablet or one 10 mg OCA tablet, or matching placebo).

Investigational product will be taken orally, up to once daily, for the duration of the study.

All subjects will be instructed to begin dosing on the day after the Day 0 visit (ie, on Day 1) and to take investigational product at approximately the same time of day. Subjects must be instructed to swallow the tablet whole; they must not chew, divide, or crush the tablet.

At each study visit where the daily dose of investigational product is administered at the site, all assessments, except for the post-dose collection of blood samples for the subset of subjects participating in the Month 9 PK assessment, must be completed before administration of investigational product.

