13.1.2. Determination of Sample Size

The following assumptions were used in sample size calculations:

- Exponential survival curves, placebo survival estimate of 0.6 at 8 years with a hazard ratio of 0.60, and total study duration of 10 years (from first subject enrolled), allowing for 4 years subject accrual and 6 years of follow up.
- Subjects will be randomized in a 1:1 ratio to placebo or OCA.
- The 2 groups will be compared using a 2-sided log rank test at the 5% level of significance.
- Two interim analyses and one final analysis are planned.

Based on the randomization ratio, significance level, and assumed hazard ratio, a total of 127 events (both groups combined) will provide 80% power to demonstrate a statistically significant difference between OCA and placebo on time to liver-related outcomes, including all-cause mortality.

In addition, based on the remaining assumptions stated above, it is estimated that approximately 428 subjects will be enrolled to attain 127 events.

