13.1.10. Multiple Comparisons/Multiplicity

The key secondary efficacy endpoints are as follows:

- Time to MELD score ≥ 15
- Time to first occurrence of liver transplant or death (all-cause)
- Change from Baseline in total bilirubin at end of study
- Change from Baseline in ALP at end of study

The hypothesis testing of key secondary analyses will compare placebo and OCA and will be conducted in a sequential closed testing gate-keeping procedure (in the order in which the key secondary endpoints are stated above), provided that the primary efficacy endpoint comparison is statistically significant in favor of OCA. If the primary comparison is not statistically significant then comparison of the secondary endpoints will be considered as descriptive and exploratory. This procedure controls the study-wise type I error.

- First (step 1) placebo and OCA will be compared with respect to the primary efficacy endpoint. If the comparison achieves statistical significance at 2-sided 0.05 level in favor of OCA group, then
- The time to MELD score ≥ 15 will be compared between placebo and OCA (step 2). If the comparison achieves statistical significance at 2-sided 0.05 level in favor of OCA group, then
- The time to liver transplant or death (all-cause) will be compared between placebo and OCA (step 3). If the comparison achieves statistical significance at 2-sided 0.05 level in favor of OCA group, then
- Change from Baseline in total bilirubin will be compared between placebo and OCA (step 4). If the comparison achieves statistical significance at 2-sided 0.05 level in favor of OCA group, then
- Change from Baseline in ALP at the end of study will be compared between placebo and OCA (step 5).

If at any step defined above the comparison is not statistically significant at the 2-sided 0.05 level then the remaining comparisons in the stated hierarchy will be considered descriptive and exploratory. The study-wise type I error will be maintained with the above closed procedure.

Additional efficacy endpoints will be analyzed; however, hypothesis tests will be applied for descriptive and exploratory purposes only.

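### Section 13.1.5 names the Sign Test as a fallback for comparing OCA with placebo, but that test needs paired or one-sample data and the two arms are independent.

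*Protocol*

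**What the plan says.** The last paragraph of Section 13.1.5 covers changes in MELD score, Child-Pugh score, Mayo Risk Score, IgM, CRP, TNF-alpha, FGF-19, CK-18, C4 and ELF score, ten measures in all. These "will be summarized and analyzed using the Wilcoxon Rank Sum Test to compare treatment groups". For the effect estimate, "The median differences and 95% CI of the median differences between treatment groups will be constructed using Hodges-Lehmann" is specified. The paragraph then closes with the fallback: "If the median differences between treatments are not symmetrical around the median, the Sign Test may be used".

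The design is a parallel-group trial. Section 9.1 states "Two treatment groups will be evaluated: OCA and placebo", and Section 13.1.2 states "Subjects will be randomized in a 1:1 ratio to placebo or OCA".

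On the status of these measures, Section 13.1.10 sets out the hierarchy for the primary and four key secondary endpoints and then says "Additional efficacy endpoints will be analyzed; however, hypothesis tests will be applied for descriptive and exploratory purposes only".

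All of this is body text of Version 3.1 (23 December 2016). The synopsis of Version 4 (10 May 2017) is also in the file, but the text of its Section 13.1.5 is not.

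**The concern.** The rank sum test and the two-sample Hodges-Lehmann estimate are methods for two independent groups. The Sign Test is a method for one set of differences. The fallback sentence speaks of differences between treatments, so on its face it puts a one-sample method in place of a two-sample one for the OCA-versus-placebo comparison.

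An analyst who followed the sentence would have two ways to produce a number. One is to run the Sign Test on change from baseline within each arm. That answers whether the arm changed, and could be reported as if it answered whether the arms differ. The other is to pair OCA and placebo subjects by some arbitrary rule, and the p-value would then depend on that rule.

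Markers of inflammation and fibrosis are a stated secondary objective (Section 6.2), and this paragraph is where their laboratory markers get their between-arm analysis.

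**Working it through.** No figure in the plan rests on this sentence, so there is nothing to reproduce. The check is whether the test fits the design. A small illustration follows, with 214 per arm (428 / 2 from Section 13.1.2) and distributions that are assumed, not taken from the protocol.

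**1. What each test needs.**
- Sign Test: differences D_1, ..., D_n, one per pair (or one value per subject against a fixed median). The statistic is S = number of D_i > 0, referred to Binomial(n, 1/2).
- Rank sum test: X_1, ..., X_m in one arm and Y_1, ..., Y_n in the other. The statistic is equivalent to U = number of pairs (i, j) with Y_j > X_i, taken over all m × n between-arm pairs.

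**2. What the design supplies.** There are two arms, randomized 1:1, stratified by UDCA use and bilirubin category (Section 9.4), with no matching of OCA to placebo subjects. The matching in Section 13.1.8 concerns historical controls. So there is no D_i for OCA versus placebo, and S is not defined for that comparison.

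**3. If pairs are made up.** With 214 per arm there are 214 × 214 = 45,796 between-arm pairs. The rank sum test uses all of them; a Sign Test on one arbitrary pairing uses 214. One fixed data set was drawn (log-normal, log-scale SD 1, log-scale means 0 and 0.25) and re-paired at random 5,000 times:

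| Analysis of the same data | p-value |
|---|---|
| Rank sum test | 0.0002 |
| Sign Test, smallest over pairings | 0.000001 |
| Sign Test, median over pairings | 0.003 |
| Sign Test, 95th percentile | 0.047 |
| Sign Test, largest over pairings | 0.31 |

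The data did not change between rows; only the pairing did.

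**4. If it is run within an arm.** Suppose both arms drift by the same 0.3 SD from baseline, so there is no treatment effect. For normal changes in the OCA arm, P(change > 0) = Φ(0.3) = 0.618. The expected count is 214 × 0.618 = 132, against 107 under the Sign Test null. The test rejected in 94% of 2,000 simulated trials. It detects drift, not a difference between arms.

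**5. Does asymmetry spoil the rank sum test?** Its null is that both arms have the same distribution. Under that null Y − X and X − Y have the same distribution, so between-arm differences are symmetric about zero however skewed the marker is. With both arms log-normal (log-scale SD 1), the rank sum test rejected in 5.1% of 5,000 simulated null trials at the nominal 5%. Symmetry of differences about the median is an assumption of the paired signed-rank test, not of this one.

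**6. What asymmetry can signal.** If OCA only shifts the distribution by Δ, between-arm differences are symmetric about Δ and the Hodges-Lehmann estimate is also the difference in medians. If they are not symmetric, a pure shift fails. The Hodges-Lehmann estimate is then still the median of between-arm pairwise differences, but may not equal the difference in medians. A Sign Test does nothing about that.

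**The case against.** The best defence has four parts.

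- **The consequence is small.** The sentence says the test may be used, and Section 13.1.10 makes hypothesis tests on these measures descriptive and exploratory. This stands, and it sets the severity.
- **The trigger is not empty.** The sentence follows directly on the Hodges-Lehmann estimate, and asymmetry of between-arm differences does bear on how that estimate is read (step 6). This stands too. It would be too strong to call the trigger meaningless; the fault is in the response to it.
- **The text may be superseded.** The sentence is from Version 3.1, and Section 13.1.5 of Version 4 is not shown. This stands as a limit on the point: whether the sentence persists must be checked.
- **The SAP will settle the choice of test.** Section 13 requires an SAP with the specific tests, approved before database lock and unblinding. A reader might infer from the loose trigger that the sponsor could pick the test after seeing the results. The protocol does not support that inference, because fixing an optional trigger is ordinary SAP content and the SAP is not at hand. What the SAP cannot do is make a paired test fit unpaired arms.

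A reader might also try to put a power cost on the fallback. The two-sample median test has efficiency (2/π)/(3/π) = 0.667 against the rank sum test for normal data, so 428 subjects would act like 428 × 0.667 = 285. That figure should not be used. The protocol never names the median test. The trigger is asymmetry, so a normal-theory ratio is out of place. The ratio also depends on the distribution and becomes 4/3, in favour of the median test, for double-exponential data.

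**Conclusion.** The point holds in a narrow form. As written in Version 3.1, Section 13.1.5 names a paired or one-sample test for a comparison of two independent, unpaired arms, in answer to a condition that does not invalidate the rank sum test under the null.

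The severity is minor. Ten secondary measures are affected, all outside the gatekeeping hierarchy, and the fallback is optional. A reader might infer a threat to the trial's main conclusions because MELD is on the list. Only change in MELD score is involved here; the time-to-MELD endpoints use the stratified log rank test of Section 13.1.3. The primary analysis, the key secondary analyses, type I error control and the sample size are unaffected.

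The conclusion rests on the parallel-group design and on the absence of any OCA-placebo pairing in the text at hand. It does not depend on the simulated figures, which only illustrate it under assumed distributions.

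**What to change.** Delete the Sign Test sentence from Section 13.1.5. Check Section 13.1.5 of Version 4 and the SAP, and delete it there if it is repeated.

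Keep the rank sum test and the Hodges-Lehmann estimate with its 95% CI, and describe the estimate as the median of the between-arm pairwise differences. That description stays correct when a pure location shift does not hold.

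If a fallback is still wanted, name a two-sample method, such as Mood's median test, with a trigger fixed before unblinding.

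The cost is one deleted sentence and a short clarification. No data collection, sample size or primary analysis changes.
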